6.3.9 Multiple surveys

Initial survey data processing revealed that some patients began multiple Admission surveys. Specifically, 322 patients had more than one survey, with a total of 719 multiple surveys. These cases were commonly related to technical issues with the Qualtrics survey system experienced by the patient, for example in the case of a loss of wireless connectivity. In these cases, patients would frequently log back into the system and attempt to complete the survey again. The research team developed a set of heuristics to determine which survey responses to keep (see Table 3).

Table 3. Multiple survey heuristics.

Rule	Cause	Description	Potential reason	Number of surveys dropped
1	Empty surveys	If a patient had multiple surveys and at least one was non-empty, the empty surveys were dropped.	Loss of connectivity could have created multiple empty survey records.	228
2	Paper surveys	When a patient had both electronic and paper survey, the electronic survey was dropped.	Patients started an electronic survey and then changed their preference and asked for paper.	94
3	Intervention check	When a patient had more than one survey attempt, the survey attempt that occurred in the same admission as the study intervention or interaction with the study team was kept.	Patients were discharged before the study team was able to perform an intervention. Subsequently, they were readmitted, attempted a new survey, and received an intervention or interacted with the study team. The first survey was discarded.	11
4	Recent admission	When a patient had more than one survey, the survey attempt from the most recent admission was kept.	Patients with multiple admissions and multiple survey attempts that did not receive an intervention or interaction with the study.	4
5	Completion rate	For patients who still had more than one survey attempt, only surveys with greater than 60% completion rate were kept.	Patients with multiple survey attempts within a single admission.	5

In the 71 cases where a participant completed more than one survey at greater than 60%, the research team adopted the following question level heuristic to identify the patient's answer:

1. If a question was completed in only one survey attempt, that response was kept
2. If a question was the same in all survey attempts, that response was kept
3. If a question response was ever in conflict, that response was treated as missing

6.3.10 Missing Touch intervention date

The date of receipt of a High-Touch intervention was supposed to be recorded for each patient in Qualtrics in an administrative data system. In rare instances, this date was missing. For these instances, intervention delivery date was identified from study notes made by the TNs about patient visits that included dates and details of encounters and was entered manually.

Section 7: References

4. US Department of Health Human Services. Multiple chronic conditions—a strategic framework: optimum health and quality of life for individuals with multiple chronic conditions. Washington, DC: US Department of Health and Human Services 2010;2.

## Section 1: Statistical analysis

### 1.1 Confidence intervals and p-values

For all statistical tests, a p-value of 0.05 was used to assess significance and 95% confidence intervals were reported. No adjustment was done for multiple hypothesis testing.

### 1.2 Missing data

All available data was used for the analysis. Missing data was treated as missing completely at random (MCAR). No imputation was used.

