3.1.3 Allocation ratio

The Tech intervention contrasted two function sets—Lite-Tech (40% allocation), which was a minimalistic toolset focused on providing basic data to the patient, and Full-Tech (60% allocation), a more expansive toolset. The Touch intervention contrasted two training approaches—Low-Touch, a self-guided approach where patients could view built-in tutorials, and High-Touch (initially 50% allocation), where patients receive in-person guided training with the technology. The realized allocation ratios are presented in Table 2.

Table 2. Realized allocation ratio.

Tech Allocation	Touch Allocation		Total
	High	Low	
Full			
Frequency	624	1,523	2,147
Row %	29.1%	70.9%	100.0%
Column %	69.3%	76.5%	74.2%
Overall %	21.6%	52.7%	74.2%
Lite			
Frequency	277	468	745
Row %	37.2%	62.8%	100.0%
Column %	30.7%	23.5%	25.8%
Overall %	9.6%	16.2%	25.8%
Total			
Frequency	901	1,991	2,892
Row %	31.2%	68.8%	100.0%
Column %	100.0%	100.0%	100.0%
Overall %	31.1%	68.8%	100.0%

The assignment protocol used three phases where the Touch allocation ratio was changed by the research team.

1. In Phase 1, patients received the High-Touch intervention only after consenting to the study and submitting their Admission survey (see Section 3.8.2). Low-Touch patients could view the tutorial at any point and were not required to complete the Admission survey. Phase 1 assigned patients to High/Low-Touch in a 1:1 ratio.
2. In Phase 2, beginning in February 2018, the study shifted to a 3:1 ratio of High/Low-Touch. This change was done to ensure that sufficient individuals were assigned to the High-Touch intervention due to under-enrollment. Quality monitoring of the study found a number of exogenous factors that were impacting the High-Touch intervention, including, but not limited to: patient discharges; patient moved to other rooms; patient not present during TN rounding; patient was engaged with the care team and unable to work with the TN; and tablet returned prior to receiving an intervention. This change in the ratio was intended to increase the number of patients who would be eligible to receive a High-Touch intervention while maintaining the *per protocol* approach in that these exceptions were considered a component of the Protocol.

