3. Phase 3 began in March 2018 and lasted through the end of the study in September, 2018. This phase maintained the 3:1 split, but removed the requirement that patients complete the Admission survey prior to receiving the High-Touch intervention. Completion of the survey was found to limit the number of patients in the High-Touch study arm. This change represented a deviation

from the original protocol which had required that the Admission survey be completed prior to intervention delivery (see Section 4.2.1).

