4.2.1 Operational protocol amendments

Operational protocol amendment 1: Improve enrollment yield (Jan 2017)

A research team member could visit the patient to remind them to complete the survey, limited to three visits per patient, once per day. Patients without completed surveys could also be visited on subsequent hospital admissions to complete their survey.

Operational protocol amendment 2: Improve data quality (Jul 2017)

A confirmation was added to each page of the survey to inform respondents when they had left questions unanswered on a page. They could continue to advance if that was their preference.

Operational protocol amendment 3: Intervention available after consent (Feb 2018)

TNs were allowed to make first contact for the High-Touch intervention once the patient consented—no longer waiting for a complete Admission survey. The TN should work with the patient to walk them through completing the survey during the intervention.

Operational protocol amendment 4: Intervention assignment (Mar 2018)

Individuals that had activated a MyChart Bedside account or were in a Full-Tech unit prior to the study start were manually assigned Full-Tech regardless of their MRN.

Individuals who were found to have accessed both Full and Lite versions over the course of the study were to be excluded from the analysis for this study.

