### 1.6.1 Outcome 1 – Patient satisfaction was dependent on treatment

*Outcome specification:* Variations of this outcome were available in each survey. The following 5-point Likert scale survey items were explored as individual items dichotomized to one “most positive” response versus all other responses:

- **15-day Post-discharge survey:** In your most recent hospital experience, how satisfied were you with the interactions you had with your healthcare professionals?
- **15-day Post-discharge survey:** In your most recent hospital experience, how satisfied were you with how well your healthcare professionals responded to your concerns?
- **6-month Post-discharge survey:** In the past six months, how satisfied were you with the interactions you had with your healthcare professionals?
- **6-month Post-discharge survey:** In the past six months, how satisfied were you with how well your healthcare professionals responded to your concerns?

*Statistical Model:* Logistic regression models with and without an interaction of Tech and Touch were reported.

*Covariates:* The corresponding survey item from the Admission Survey was used as a covariate for the items listed above. The two relevant survey items were:

- **Admission survey:** In the past 12 months, how satisfied were you with the interactions you had with your healthcare professional?
- **Admission survey:** In the past 12 months, how satisfied were you with how well your healthcare professionals responded to your concerns?

*Sub-sample analysis:* No sub-sample analyses were considered for this outcome.

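### The satisfaction models (H2 Outcome 1) drop patients without the Admission item under an MCAR assumption, although the protocol links completion of that survey to Touch and calendar time

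*SAP*

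**What the plan says.** On missing data, SAP 1.2 says that all available data are used, that "Missing data was treated as missing completely at random (MCAR", and that "No imputation was used". No sensitivity analysis for missing data appears in either document.

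H2 is one of the two primary hypotheses (Protocol 2.2). SAP 1.6.1 tests satisfaction with four post-discharge items, each dichotomised and fitted by logistic regression. On covariates it says: "The corresponding survey item from the Admission Survey was used as a covariate for the items listed above". SAP 1.4.1 makes intention-to-treat the main population.

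The protocol describes how the Admission survey was handled:

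- Protocol 3.1.3, Phase 1: "patients received the High-Touch intervention only after consenting to the study and submitting their Admission survey", whereas "Low-Touch patients could view the tutorial at any point and were not required to complete the Admission survey".
- Protocol 3.1.3, Phase 3 (from March 2018): the study "removed the requirement that patients complete the Admission survey prior to receiving the High-Touch intervention", because "Completion of the survey was found to limit the number of patients in the High-Touch study arm".
- Protocol 4.2.1, amendment 3 (February 2018), on the High-Touch visit: "The TN should work with the patient to walk them through completing the survey during the intervention".
- Protocol 4.2.1, amendment 2 (July 2017): an on-page prompt for unanswered questions was added.
- Protocol 3.1.3, Phase 2 (February 2018): Touch allocation changed from 1:1 to 3:1.

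**The concern.** MCAR requires that missingness be unrelated to arm, calendar time and patient. For the Admission survey the protocol describes procedures that tie completion to Touch and to time.

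This matters most where the Admission item is a covariate. A logistic fit without imputation cannot use a patient whose covariate is missing, even if that patient answered the 15-day or 6-month survey. Touch is assigned at or before consent (Protocol 3.2.2 and 3.3) and the survey follows consent (Protocol 5.2.1). Completion is thus a post-randomisation event, and restricting the model to completers weakens the intention-to-treat comparison that SAP 1.4.1 promises. A Touch effect on satisfaction could be created or hidden in a primary hypothesis.

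**Working it through.** **1. The plan's own yardstick.** Protocol 3.4 gives 3,872 patients and detectable changes of 2.2% to 3.8%, but not power, sidedness or baseline rates, so the figure cannot be strictly reproduced. It is compatible with two-sided 0.05, 80% power and 1:1 allocation (1,936 per group), using Δ = 2.80 × √[(p₁(1−p₁) + p₂(1−p₂))/1,936]:

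- p₁ = 0.749, p₂ = 0.787: 2.80 × √(0.3556/1,936) = 0.038.
- p₁ = 0.925, p₂ = 0.947: 2.80 × √(0.1196/1,936) = 0.022.

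I use 2.2 to 3.8 points as the size that matters.

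**2. Which models lose patients without the Admission item?**

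- H2 Outcome 1 (SAP 1.6.1): Admission item is a covariate. Yes.
- H2 Outcomes 2a and 2b (SAP 1.6.2a, 1.6.2b): 15-day items, no covariates. No.
- H4 (SAP 1.8.1): no covariates. No, for the 15-day and 6-month results.

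**3. How large could the bias be?** The documents give no completion rates, so every rate here is an assumption. Let U be a standard normal patient trait, with no true Touch effect:

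- Outcome: logit P(top-box) = 1.21 + 0.7U, which gives 75% overall.
- Completion: logit P(complete) = a + gU, with a set to give the assumed completion rate in each arm.
- Top-box rate among completers = E[P(complete) × P(top-box)] / E[P(complete)], by numerical integration over U.

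| Completion, Low vs High | g | Top-box Low | Top-box High | High − Low (points) |
|---|---|---|---|---|
| 60% vs 80% | 0 | 75.0% | 75.0% | 0.0 |
| 60% vs 80% | 0.5 | 77.3% | 76.2% | -1.1 |
| 60% vs 80% | 1.0 | 79.1% | 77.2% | -1.9 |
| 60% vs 90% | 0.5 | 77.3% | 75.6% | -1.7 |
| 60% vs 90% | 1.0 | 79.1% | 76.2% | -2.9 |
| 80% vs 60% | 0.5 | 76.2% | 77.3% | +1.1 |
| 80% vs 60% | 1.0 | 77.2% | 79.1% | +1.9 |
| 60% vs 60%, g = 0 in High only | 1.0 (Low) | 79.1% | 75.0% | -4.1 |

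The last row represents navigator help that removes the selection in High-Touch but not in Low-Touch. Adjusting for the Admission item does not remove the bias: the adjusted odds ratio is 0.94 to 0.90 for 60% vs 80% and 0.92 to 0.86 for 60% vs 90%, against a true value of 1.

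**4. Phase.** No SAP model contains phase. Let f be the share of patients enrolled in Phases 2 and 3. With equal completion, the share of each arm from those phases is:

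- High: 0.75f/(0.75f + 0.5(1−f)).
- Low: 0.25f/(0.25f + 0.5(1−f)).

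For f = 0.2 these are 0.273 and 0.111; for f = 0.4 they are 0.50 and 0.25. An assumed drift in satisfaction of 2 to 5 points between periods then gives 0.162 × 2 = 0.3 to 0.25 × 5 = 1.3 points. If High-Touch completes at 90% in Phases 2 and 3 and everyone else at 60%, the High shares become 0.36 and 0.60, and the result is 0.249 × 2 = 0.5 to 0.35 × 5 = 1.8 points.

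**The case against.** The strongest reply is that dependence on arm alone does no harm: a regression containing Touch is not biased by completion that differs only by Touch. That stands, and the g = 0 row shows it. Bias needs completion to relate also to satisfaction, differently by arm. The documents neither show nor exclude this.

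Four further points also stand:

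- **Phase 1.** A reader might infer that the Phase 1 rule made completion depend on randomised arm. What it directly did was make receipt of High-Touch depend on the survey. All participants were to take the survey straight after consent (Protocol 5.2.1), and patient and navigator were blind to assignment at consent (Protocol 3.3). The walk-through is the clearest effect of arm on completion.
- **Help in one arm only.** The walk-through is written for the High-Touch visit, but the text does not say that nobody else was helped. Amendment 1 allows up to three reminder visits without naming an arm.
- **The July 2017 prompt** was not arm-specific, and allocation was 1:1 until February 2018. It links item completion to time, not to Touch.
- **A large favourable bias.** A reader might suppose that dissatisfied High-Touch patients answer less often. With 70% top-box and 50% response, cutting response to 40% or 35% among them gives 0.35/0.47 = 74.5% or 0.35/0.455 = 76.9%, a false gain of 4.5 to 6.9 points. No passage suggests that behaviour, and the walk-through points towards more completion in High-Touch. Non-response that depends on the outcome itself would also not in general be removed by imputation under missing at random.

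**Conclusion.** The concern holds for H2 Outcome 1. MCAR is not credible for its Admission covariate, nothing in the SAP tests it, and the model discards randomised patients on a post-randomisation event that can differ by Touch and phase.

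Whether the Touch estimate is actually biased, by how much and in which direction cannot be determined without completion rates by arm and phase. Several of the illustrative biases fall in or near the 2.2 to 3.8 points the design aimed to detect. They rest on the assumed completion rates, trait model and 75% top-box rate.

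A reader might extend this to all of H2 and to H4. The documents do not support that for the covariate route: under intention-to-treat, a missing Admission survey removes nobody from the post-discharge models of H2 Outcomes 2a and 2b or H4. H4 would be touched only by other routes: if the Admission wave were analysed as an outcome (SAP 1.8.1 does not name the wave), or in the per-protocol set, whose weights omit phase and survey completion.

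The conclusion takes SAP 1.4.1 as governing. Protocol 4.3 instead regroups patients by the Touch intervention received. Under that rule the survey gate could affect every outcome, so the two sections need to be reconciled.

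**What to change.** For H2 Outcome 1, amend SAP 1.2 and 1.6.1 as follows:

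- Replace MCAR with multiple imputation under missing at random, done within randomised Touch arm. Use Tech, phase, hospital, age, sex, race, Charlson index, the available survey items (including post-discharge responses) and portal use. Patients who lack the Admission item then stay in the analysis.
- Put phase in the outcome model as well as in the imputation model.
- Keep the current available-case analysis as a sensitivity analysis.
- Add a shift analysis that moves imputed responses up and down in each Touch arm, since the direction of any bias is unknown.
- Report Admission, 15-day and 6-month survey completion by randomised Touch arm and phase.

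The data model (Protocol 6.2) already covers demographic, survey, encounter and portal-use data, so no new collection is needed. The cost is more analysis and reporting work, and reliance on an imputation model whose assumptions must be stated.

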### 1.3 Statistical software

All analyses were conducted using Stata MP 14.2.

### 1.4 Assumptions and testing

#### 1.4.1 Analysis populations

Estimates of the intervention effects were calculated on two analytic populations. The main analytic population of the study used an *intention-to-treat (ITT)* approach. Using this paradigm, participants were analyzed on the basis of the study group to which they were randomized, regardless of their eventual receipt of that intervention.

The effects of the intervention were additionally evaluated on a *per-protocol* population, composed exclusively by those participants who were administered their randomized intervention. The analysis of the data from the per-protocol population was weighted by the inverse of their probability to receive the intervention to which they were originally randomized, computed on the basis of the following demographic and clinical characteristics: sex, race, age at time of enrollment, Charlson Comorbidity Index, length of stay.

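### The per-protocol weights in SAP 1.4.1 ignore the Phase 1 rule that only Admission-survey submitters could receive High-Touch, so the Phase 1 Touch contrast is selected in one arm only

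*SAP*

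**What the plan says.** SAP 1.4.1 sets out two populations. "The main analytic population of the study used an *intention-to-treat (ITT)* approach". The second is a per-protocol set, "composed exclusively by those participants who were administered their randomized intervention", weighted by the inverse probability of receiving the assigned intervention. That probability is "computed on the basis of the following demographic and clinical characteristics: sex, race, age at time of enrollment, Charlson Comorbidity Index, length of stay". The list is closed. It holds neither Admission-survey submission nor study phase.

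Protocol 3.1.3 describes who could receive Touch:

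- Phase 1 (1:1 High to Low): "In Phase 1, patients received the High-Touch intervention only after consenting to the study and submitting their Admission survey". For the other arm: "Low-Touch patients could view the tutorial at any point and were not required to complete the Admission survey".
- Phase 2 (from February 2018): allocation moved to 3:1.
- Phase 3 (March to September 2018): still 3:1, but the study "removed the requirement that patients complete the Admission survey prior to receiving the High-Touch intervention". The reason given is that "Completion of the survey was found to limit the number of patients in the High-Touch study arm".

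**The concern.** Inverse-probability weighting repairs selection into the per-protocol set only if the weight model holds the variables that drive both receipt and outcome, and only if everyone had some chance of receipt. In Phase 1 neither condition is secured. The protocol names a rule that decided receipt in one arm and says that it bit, yet the rule is absent from the weight model. A Phase 1 High-Touch participant who did not submit the survey could not be trained, so no such person remains in the set to be weighted up.

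Submission is unlikely to be unrelated to the outcomes. By default the survey was electronic and reached through MyChart Bedside (Protocol 3.8.2), and H1 counts MyChart Bedside use. People who found and submitted the survey may well use the portal more.

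What is at stake is how the second estimate is read. Agreement with the intention-to-treat result would be taken as corroboration, and a larger value as the effect of actually being trained. Neither reading is safe if part of the contrast is submitters against a mixture of submitters and non-submitters.

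**Working it through.** **1. How much non-receipt there was.** Table 2 of the protocol gives 624 + 277 = 901 High-Touch out of 2,892, and 901/2,892 = 31.2%, which reproduces the printed row percentage. Allocation was 1:1 and later 3:1, so the number assigned High-Touch should lie between 0.50 × 2,892 = 1,446 and 0.75 × 2,892 = 2,169. If Table 2 counts receipt, as the reassignment rule in Protocol 4.3 implies, receipt was between 901/2,169 = 42% and 901/1,446 = 62%, and between 545 and 1,268 assigned participants were not trained. Phase counts are not given, and these totals are after exclusions. The survey rule is one cause among several that Protocol 3.1.3 lists.

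**2. Spurious rate ratio when every per-protocol High-Touch participant was under the rule.** Assume no Touch effect and submission unrelated to the five weight variables. Let *s* be the share who submit and *k* the ratio of sessions in submitters to non-submitters. High-Touch has relative mean *k* and Low-Touch has *sk* + 1 − *s*, so

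R = k / (sk + 1 − s).

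**3. The pooled analysis.** Phase 3 had no survey requirement. If a share *w* of per-protocol High-Touch participants was under the rule, phases are otherwise exchangeable, and receipt outside the rule is unrelated to outcome, the ratio is 1 + w(R − 1).

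| s (assumed) | k (assumed) | R, all under the rule | w = 0.5 |
|---|---|---|---|
| 0.8 | 1.2 | 1.2/1.16 = 1.03 | 1.02 |
| 0.6 | 1.5 | 1.5/1.30 = 1.15 | 1.08 |
| 0.4 | 2.0 | 2.0/1.40 = 1.43 | 1.21 |

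None of *s*, *k* or *w* is in the documents.

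**4. Binary outcomes.** On the difference scale the bias is w(1 − s)d, where *d* is the outcome gap between submitters and non-submitters. With an assumed *d* of 10 points and s = 0.5, 0.7, 0.9, it is 5.0, 3.0, 1.0 points for w = 1, and 2.5, 1.5, 0.5 points for w = 0.5. For scale, Protocol 3.4 aimed to detect changes of 2.2% to 3.8% in satisfaction scores.

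**5. Which remedy works.** A simulation with no Touch effect (1,000,000 participants, all under the rule, d = 10 points, completion about 0.5, 0.7, 0.9) gave these spurious effects in points:

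| Analysis | 0.5 | 0.7 | 0.9 |
|---|---|---|---|
| Weights on baseline characteristics only | 5.2 | 2.7 | 0.9 |
| Submission added to the weight model | 5.6 | 3.0 | 1.0 |
| Both arms restricted to submitters | 0.1 | −0.4 | −0.1 |
| Intention to treat | 0.0 | −0.1 | 0.0 |

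The last two rows are zero apart from simulation noise. Adding submission to the weights does not help, because there are no trained non-submitters to weight up.

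**6. Which outcomes are exposed.** The H2a models (SAP 1.6.1) carry the matching Admission-survey item as a covariate and SAP 1.2 rules out imputation, so both arms are already limited to people who answered it. H1, H2b, H3 and H4 carry no Admission item.

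**The case against.** Several points against a stronger reading are sound.

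- **Phase.** A reader might infer that the whole per-protocol analysis sets survey completers against everyone. The documents do not support that. Phase 3 had no survey requirement, so pooled High-Touch is a mixture. Even the end date is unsettled: Protocol 3.1.3 places removal in March 2018, Protocol 4.2.1 dates it to February 2018, and Table 1 describes navigators being allowed to mark a survey as complete from 22 February, with a further change 22 days later. Only Phase 1 is certain.
- **Direction.** A reader might infer that the estimate is inflated toward benefit. That is plausible but not documented. Paper surveys were available (Protocol 3.8.2), staff made reminder visits and pages could be advanced unanswered (Protocol 4.2.1), so submission is not a pure marker of portal engagement. Other causes of non-receipt, such as discharge, room moves and tablet return, have an unknown net effect.
- **Size.** The analysed set already excludes zero-use participants and stays under three days (Protocol 6.3.8), and the models carry a provision-length offset (SAP 1.4.2). Both may narrow the gap between submitters and non-submitters.
- **Role.** This is an additional analysis; the intention-to-treat estimate does not depend on it.

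These points narrow the concern without removing it. The Phase 1 rule applied to one arm, the protocol says it limited that arm, and five baseline characteristics cannot be assumed to account for it.

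**Conclusion.** The concern holds for the Phase 1 part of the per-protocol Touch contrast, and through it for the pooled per-protocol estimates of H1, H2b, H3 and H4. It does not reach H2a in the same way, and it does not touch the intention-to-treat analysis. A reader should not conclude that the trial's main Touch result is compromised.

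Under the stated assumptions the spurious rate ratio is 1.03 to 1.43 with everyone under the rule, and about 1.02 to 1.21 with half. These figures show what is possible; they are not estimates of the bias. They rest on assumed completion, use ratio and share under the rule, on submission being unrelated to the weight variables, and on phases being otherwise exchangeable. An upward direction is plausible only. The point merits a change to the plan because the correction is cheap and the records should already be held.

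**What to change.** In SAP 1.4.1:

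1. **Fix the period.** Reconcile Protocol 3.1.3, Protocol 4.2.1 and Table 1 on what applied in February and March 2018, and define the period under the survey requirement by date. Phase 1 belongs to it in any case.
2. **Restrict both arms.** For participants enrolled in that period, limit both Touch arms of the per-protocol set to those who submitted the Admission survey. State the assumption that Touch assignment did not affect submission, since submission follows randomisation, and report submission by randomised Touch arm as a check.
3. **Account for phase** in the weight and outcome models, because both the allocation ratio and the survey requirement changed by phase.
4. **Do not put Phase 3 survey completion in the weight model.** Under Protocol 4.2.1 (amendment 3) navigators were to help participants complete the survey during the training visit, so completion there may be a consequence of receiving High-Touch.
5. **Report a phase-adjusted complier effect** with randomised Touch as instrument. Protocol 4.3 records only 3 Low-Touch participants who received training. State the assumption that assignment acts only through training.

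The cost is SAP wording and a re-fit on data already held. The per-protocol set becomes smaller, mainly in Low-Touch, intervals widen, and the Phase 1 estimate applies to survey submitters only. If the phase or submission records prove unusable, the SAP should at least state the limitation beside the per-protocol results.
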